## V. Study Procedures

### a) *Study visits and parameters to be measured:*

The study involves the enrollment of 30 outpatients with major depressive disorder.

Patients screened for the study and found to be eligible will return for their baseline visit after one week, at which eligible patients (n = 30) will be randomized to either CBT or to standard pharmacotherapy with an SSRI (escitalopram 10-20mg) for 12 weeks.

The CBT group will receive twelve weekly 50-minute individual sessions over the course of 12 weeks conducted by experienced therapists who are trained in manual based CBT. The medication group will receive open label treatment of escitalopram, 10-20 mg/day, flexible dose, for 12 weeks, and will be seen every two weeks by a study physician. In both arms, study assessors, who are blind to treatment condition, will assess patients monthly (week 0, 4, 8, and 12), and are responsible for the primary outcome measure (HAMD-17).

The QEEG will be administered 5 times during the study (week 0, 1, 2, 8 and endpoint) allowing us to assess whether there are any correlations between QEEG patterns and changes in clinical functioning. We will record EEG from a fronto-parieto-temporal derivation using a 4-channel EEG Monitor (Aspect Medical Systems) connected to the subject via disposable EEG electrodes. The adhesive material of the electrodes is similar to that found in ECG electrodes. All recordings will be analyzed off-line to generate QEEG metrics. Once such QEEG metric, the ATR, is a complex index derived from left-right asymmetry of combined theta+alpha (4-12Hz) power, relative theta power, and percent change from baseline in relative theta power, and ranges from 0 (low probability of response) to 100 (high probability of response). De-identified data will be shared with Aspect Medical Systems for offline calculation of EEG-based metrics.

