- h. ATQ-R (Kendall, Howard, & Hays, 1989): The Automatic Thoughts Questionnaire-Revised is a self-rated instrument to assess cognitive self-statements related to

depression. It includes 30 negative self-statements and 10 self-statements reflecting positive affect.

- i. PSS (Cohen et al., 1983): The Perceived Stress Scale is a self-rated instrument to evaluate a patient's level of perceived stress. Patients are asked to endorse to what degree, over the last month, they felt stressed. Each of the 14 statements presented describes a stressful state.
- j. SF36 (Ware, 1993): Medical Outcomes Study (MOS) 36 Item Short-Form Health Survey is a clinician-administered instrument to assess quality of life. It has 36 items and contains subscales that measure physical functioning, physical role functioning, social functioning, emotional role function, general health, energy, mental health, and bodily pain over the past four weeks.
- k. Snaith-Hamilton Pleasure Scale (SHAPS) (Snaith et al., 1995). This short 14-item self rated scale assesses self-reported anhedonia.

Adverse events and changes in concomitant medications will be assessed at each visit with the clinician for subjects randomized to the medication arm. The clinician will inquire about any changes in dosages of medications as well as days the medications were not taken. The importance of taking medications as prescribed and refraining from taking a « holiday » from medication on weekends or at any other time during the study will be emphasized from the time the patient enrolls in the study.

For subjects randomized to psychotherapy, adverse events will be assessed by the CBT therapist at baseline and weeks 2, 4, 6, 8, 10 and 12.

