## IX. Monitoring and Quality Assurance

a) Independent Monitoring of Source Data: Documentation of the presence of any side-effect or adverse event will be completed at every visit and will be reported in accordance with AE reporting guidelines of the MGH IRB. Patients will be encouraged to contact the investigator or a member of her staff at any time between visits concerning adverse events or worsening of symptoms. An event that is deemed serious will be recorded in the patient's study binder and will be handled in an expeditious manner. A Safety Monitoring Committee, including Drs [name], [name], and [name], will review SAEs quarterly. Research assistants responsible for data collection and storage will be aware of and comply with all regulatory requirements related to adverse events. In the event that a patient becomes ill or is injured as a direct result of study participation, medical care will be made available. All adverse events will be followed to resolution and reported to the MGH IRB as serious in the event that they are unanticipated, possibly related to the study, and meet any one of the following criteria:

1. Fatal or life threatening
2. Requires prolonged inpatient hospitalization
3. Results in persistent or significant disability or incapacity
4. Congenital anomaly
5. Medical events that require intervention to prevent serious outcome
6. Cancer
7. Overdose
8. Results in substance dependency or abuse

Outcomes Monitoring: Treatment outcomes will be documented so that at study completion appropriate recommendations can be made for further treatment.

b) Safety Monitoring:

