### Monitoring of Safety Data by the DSMB:

1. Unblinded Reporting – Safety information for this study will be reported to the DSMB in an unblinded manner. A statistical penalty will not be assessed for the ongoing unblinded review of safety by the DSMB. Unblinded data will not be released to the investigators unless necessary for safety reasons.

2. Range of Safety Reporting to the DSMB – It is considered necessary for the purpose of monitoring the safety of the study that the DSMB review not only adverse events (AEs) and serious adverse events (SAEs), but other data that may reflect differences in safety between treatment groups. This includes treatment retention rates, and reasons for drop-out, and laboratory values reflecting potential toxicity.

3. Serious Adverse Events – Expedited review will occur for all events meeting the FDA definition of Serious Adverse Events (SAEs) – i.e., any fatal event, immediately life-threatening event, permanently or substantially disabling event, event requiring or prolonging inpatient hospitalization, or any congenital anomaly. This also includes any event that a study investigator or the DSMB judges to impose a significant hazard, contraindication, side effect, or precaution.

For purposes of this study, all SAEs will be required to be reported to the DSMB, regardless of any judgment of their relatedness to the study drug. All relevant information will be reported to the DSMB for each SAE including information about the event and its outcome, dosing history of all study drugs, concomitant medications, the subject's medical history and current conditions, and all relevant laboratory data. Notification by e-mail, and FAX transmittal of all related study forms shall be made to the DSMB within 2 days of the occurrence of any SAE. Information will be reviewed and a determination made of whether there was any possible relevance to the study drug. Additional reporting to local IRBs will be done within 24 hours of the SAE.

4. Non-Serious Adverse Events – At periodic intervals (quarterly during the course of the study and then again at its completion), the DSMB will be provided with un-blinded summaries of the numbers and rates of adverse events by treatment group. These reports will include types of events, severity, and treatment phase. Data on individual non-serious adverse events is not expected to be needed for this review.

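### Routine enquiry about new concomitant medication is specified for the drug arm only, so a psychotropic started by a CBT patient has no scheduled route to detection

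*Protocol*

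**What the plan says.** Protocol section V(a) sets out follow-up enquiry separately for each arm. For drug-treated patients: "Adverse events and changes in concomitant medications will be assessed at each visit with the clinician for subjects randomized to the medication arm". These patients "will be seen every two weeks by a study physician". For psychotherapy patients the corresponding text is one sentence: "adverse events will be assessed by the CBT therapist at baseline and weeks 2, 4, 6, 8, 10 and 12". It does not mention medication. On contact in that arm, the protocol states: "The CBT group will receive twelve weekly 50-minute individual sessions over the course of 12 weeks".

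Freedom from psychotropics matters at entry. Inclusion criterion 5 requires four drug-free weeks before screening. Exclusion criteria 4 and 5 rule out current psychotropics and certain other agents, among them beta-blockers.

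Section IX(a) gives a general rule that does not distinguish the arms: "Documentation of the presence of any side-effect or adverse event will be completed at every visit". Under section IX(b), the DSMB receives "un-blinded summaries of the numbers and rates of adverse events by treatment group" each quarter and at completion. Each serious adverse event report must include "dosing history of all study drugs, concomitant medications", whichever arm the patient is in.

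**The concern.** The entry criteria treat psychotropic-free status as a condition for interpreting the EEG and the mood response. After randomisation, the procedures provide for routine checking of medication in one arm only, and it is not the arm that Primary Aim 1 concerns.

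Primary Aim 1 compares QEEG change between CBT responders and non-responders. Primary Aim 2 asks whether the QEEG correlates of CBT differ from those of an SSRI. The SAP summary expects antidepressant responders to show reduced theta activity and a higher ATR at about week 1. On that premise, an unrecorded antidepressant start in a CBT patient could move the predictor and the outcome together, and could make a CBT response look like a drug response. The analyst would have no routinely collected variable with which to identify that patient.

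A secondary matter is safety reporting. The DSMB sees event rates by arm, but a study clinician elicits events in one arm and the patient's own therapist in the other. No common form or set of questions is described.

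**Working it through.** No figure in the plan underlies this point, so the check sets the passages side by side and then sizes a single case.

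**1. Timing of adverse-event checks.** Medication arm: physician visits every 2 weeks over 12 weeks, 12/2 = 6, at weeks 2, 4, 6, 8, 10 and 12. CBT arm: the listed post-baseline weeks are the same 6. Counting baseline gives 7 and 7, if the medication arm has a clinician contact at baseline, which section V(a) does not spell out. The planned schedules coincide.

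**2. Content of the checks (section V(a)).**

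| | Medication arm | CBT arm |
|---|---|---|
| Who asks | clinician | treating therapist |
| Adverse events | yes | yes |
| Concomitant-medication changes | yes | not stated |

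**3. Other routes by which a new drug could come to light in the CBT arm.**
- The blinded assessors' instruments in section V(a) include no medication record.
- Toxicology is listed with the Screen Visit tests and covers drugs of abuse.
- Section IX(b) item 3 requires concomitant medications, but only when a serious adverse event has occurred.
- Section IX(a) invites patients to call about adverse events or worsening symptoms. That is unscheduled and not directed at medication.

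Detection is therefore possible, but no routine step provides for it.

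**4. What a start would affect.** QEEG is recorded at weeks 0, 1, 2, 8 and endpoint.
- Start between week 0 and week 2: can affect the Hypothesis 1 predictor (change from the beginning to two weeks) and the HAMD-17 response.
- Start after week 2: cannot affect that predictor, but can affect the HAMD-17 response. It can also affect the week 8 or endpoint EEG, which enters the SAP's analysis of change across time.

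**5. Size of one case.** 30 patients randomised 1:1 gives 30/2 = 15 per arm, and 1/15 = 6.7%. If 40% to 60% of CBT patients respond (assumption), there are 15 × 0.40 = 6 to 15 × 0.60 = 9 responders. One affected responder is then 1/9 = 11% to 1/6 = 17% of that group. These are shares of patients; they do not measure the bias in any test.

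**6. Section V(a) against section IX(a).** Section V(a) gives 6 post-baseline checks in the CBT arm. If the general rule in section IX(a) takes in each weekly session, it gives up to 12, against 6 physician visits in the medication arm. The text does not say which applies.

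**The case against.** The strongest reply is that the protocol is silent about medication in the CBT arm and does not forbid asking. A therapist who meets the patient weekly may well hear of a new prescription, and a serious event would bring it out. That stands, and it is why the point is put as no scheduled route to detection. It does not show that such starts would be missed. The exclusion criteria also concern use at entry. The effect on Hypothesis 1 is confined to starts in the first two weeks. This is a 30-patient pilot whose aims are predictive, so comparative safety is not its purpose. These arguments limit the size of the problem, but they do not supply the missing data item.

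Several stronger readings are tempting and are not supported:

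- A reader might infer that the arms are checked for adverse events on different visits or at different frequencies. The two-weekly physician visits rule that out for the planned schedule.
- A reader might set the CBT checks against the number of CBT sessions and conclude that this arm is under-observed. That comparison is within one arm and says nothing about comparability between arms.
- A reader might infer a spurious ratio of event rates from therapist elicitation. The documents give no detection rate for either kind of staff, and even the direction is unknown: a therapist with weekly contact could elicit more events than a physician.
- A reader might suppose a formal safety comparison is planned. Section IX(b) item 2 does have the DSMB review "other data that may reflect differences in safety between treatment groups", but the by-arm summaries are descriptive and neither document specifies a between-arm test of adverse events.

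Finally, the SAP is dated 12/7/2017 and describes its methods in the past tense, so collection may be over. That limits what can still be changed.

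**Conclusion.** The point holds as a gap in data collection. Routine assessment of concomitant-medication changes is specified for the medication arm and not for the CBT arm, although psychotropic-free status is an entry condition for both. One undetected start would involve about 7% of the CBT arm. It could affect the HAMD-17 response at any time before endpoint, the Hypothesis 1 QEEG change if it came before week 2, and the SAP's later-visit changes if it came afterwards.

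This rests on two assumptions: that the procedures are followed as written, and that a psychotropic can shift the EEG and mood measures, which the SAP's own expectation for antidepressants implies. The documents give no frequency for such starts, so no expected bias can be calculated. No stated figure in the plan is wrong because of this. The difference in staff between arms is a minor caveat on the DSMB summaries, and the mismatch between sections V(a) and IX(a) is a matter of wording to reconcile. Overall this is a cheap and worthwhile improvement, not a fatal flaw.

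**What to change.** 1. At the existing CBT adverse-event checks (baseline and weeks 2, 4, 6, 8, 10 and 12), record concomitant-medication changes, with start dates, and adverse events. Use the same form and questions as in the medication arm.
2. Repeat the CBT responder versus non-responder QEEG analysis without patients who started a psychotropic. Report it beside the main analysis and do not let it replace that analysis: starting a drug may itself follow from poor response, so the exclusion is selective.
3. Reconcile sections V(a) and IX(a) by stating whether the general documentation rule covers every weekly CBT session.
4. Note in the by-arm DSMB summaries that different staff elicited events in each arm. A shared form makes the questions alike but does not remove this difference.

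If collection has ended, items 1 and 3 can no longer change the data. In that case, state the gap as a limitation and run item 2 on any CBT patient whose records show a psychotropic start.

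The cost is a few minutes at visits already planned, one shared form and one extra sensitivity analysis. No visits or staff are added.

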#### Safety Data

The following laboratory tests will be performed at the Screen Visit for only those patients randomized to the medication arm (with the exception of toxicology and pregnancy test, see below):

- a. Complete Blood Count with differential (at week 4 as well)
- b. Urinalysis
- c. Clinical Chemistry (serum concentrations of electrolytes, BUN, creatinine, SGOT, SGPT, alkaline phosphatase, total bilirubin, albumin, total protein, uric acid, glucose, and cholesterol)
- d. Electrocardiogram (EKG)
- e. Urine pregnancy Test (For patients in both arms, at Screen and Week 12 or endpoint)
- f. Toxicology (patients in both arms will be screened for drugs of abuse)

The routine laboratory tests (complete blood count, urinalysis, clinical chemistry tests) will be performed by Massachusetts General Hospital Clinical Laboratories. Significantly abnormal laboratory values will be those falling outside of the normal range for the laboratory and deemed to be clinically significant by the study physicians.

For patients in both groups, weight, oral temperature, and standing and supine pulse and blood pressure (Vital Signs) will be recorded at the screen visit (and at every visit thereafter for patients in the medication arm. For patients in both groups, a physical exam will be performed at screen.

In the case of early termination, patients in both groups will be asked to return for a final study visit within 48 hours of leaving the study. All Week 12 study procedures will be completed at the time of the early termination visit.

b) *Drugs to be used:*

Patients randomized to receive escitalopram will receive open-label treatment with escitalopram, 10-20 mg/day, flexible dose, for 12 weeks. Dose selections will be determined by the study physician.

c) *Devices to be used:*

None.

d) *Procedures:*

None.

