## I. Background and significance

### A. *Treatment of MDD:*

Over two-thirds of patients with MDD treated with first-line medications, such as citalopram, fail to achieve remission during 12 weeks of acute treatment. Patients who fail to achieve remission typically have greater impairment of social and work function and a much higher risk of relapse and recurrence of MDD than those who remit (Paykel et al., 2005). As demonstrated in the STAR\*D trial, many patients who go on to achieve remission on pharmacotherapy or CBT do not do so until the second 6 weeks of treatment even with enhanced, measurement-based care (Rush et al., 2006).

Recently, an increasing body of “predictor studies” has emerged which aims to use neuroimaging measures to predict treatment outcomes. These studies are pivotal in advancing treatment options for depression, as validated surrogate markers that predict response at baseline or soon after starting treatment would help clinicians optimize a patient’s treatment within the first several weeks of initiation, potentially saving weeks to months of ongoing distress, disability and risk of suicide. In light of the challenges that MDD poses to clinicians and patients alike, identifying biomarkers which are able to predict outcome are urgently needed to help further refine the standard of care for depression. Additionally, to our awareness no studies have used neuroimaging measures to directly compare different psychosocial interventions, such as Cognitive Behavioral Therapy (CBT).

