## **II. Specific Aims:**

Primary Aim 1: To determine whether QEEG technology can predict whether a patient with MDD will respond to CBT.

Hypothesis 1: Clinical response (defined as >50% change in HAMD-17 from beginning to endpoint) will correlate with changes in QEEG metrics (ATR, EEG Bispectrum, cordance estimates) from beginning to two weeks after starting treatment.

Primary Aim 2: To determine whether there are unique biological changes in patients undergoing CBT, as measured by the QEEG, that are different than those associated with antidepressants (SSRIs).

Hypothesis 2: QEEG parameters, different from those that predict response to pharmacotherapy, will be associated with response to CBT.

Secondary Aim 1: To determine whether there are correlations between QEEG patterns and changes in clinical functioning, assessed by clinical and self-rated instruments (SF-36, Symptom Questionnaire, Beck Depression Inventory), in both arms (CBT vs. escitalopram).

Secondary Aim 2: To determine whether there are any correlations between QEEG metrics and clinical variables (gender, age, comorbid anxiety, chronicity of depression).

Secondary Aim 3: To determine whether the behavioral processes associated with reward responsiveness in a depressed population change as a function of treatment.

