## VI. Statistical Analysis

- a) *Statistical Plan:* The Mann-Whitney U test will be used to analyze differences in changes of QEEG between responders and non-responders to CBT. We will use logistic regression with the outcome being response/no response on the HAMD-17 and the predictors being other EEG measures. We will test the predictors in a stepwise manner given the limited power with a small N. A power calculation based on a previous QEEG study conducted in our clinic reveals that, to achieve power = 0.80, we would need 34 subjects per group. With N = 30 per group (60 subjects total), our power is 0.76. Power for the current study, with N = 15 per group, is 0.47. While this study is underpowered due to the small N, the goal of this study is to act as a pilot study which can help measure effect sizes, providing a foundation for future, larger projects.

For secondary aims, we will use Pearson r's for pairs of continuous measures, or point-biserial r for pairs of dichotomous and continuous measures.

Data from the Signal Detection Fact Task will be analyzed by [name] at Harvard University. Response bias will be the main variable of interest, whereas reaction time, hit rates, and discriminability values will provide control variables. Analyses of variance (ANOVAs) will be used to investigate variables across the three blocks. Discriminability and response biases will be computed using standard formulae (e.g. McCarthy and Davidson 1981).

- b) *Study Endpoints:* Endpoints will be defined as the final study visit at the end of the 12 weeks, or the termination/final visit for patients who choose to (or have to) end participation in the study prematurely.

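### Response has no fixed time for early leavers: the protocol reads it at the exit visit, the SAP analyses undefined completers, and no HAMD-17 after exit is described

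*Protocol*

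**What the plan says.** **Response.** Hypothesis 1 (Protocol, II. Specific Aims) has clinical response "defined as >50% change in HAMD-17 from beginning to endpoint", with no week attached. The predictor is the QEEG change "from beginning to two weeks after starting treatment".

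**Endpoint.** Protocol VI, b) Study Endpoints takes the visit at the end of 12 weeks, "or the termination/final visit for patients who choose to (or have to) end participation in the study prematurely".

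**Exit visit.** Under Safety Data, "patients in both groups will be asked to return for a final study visit within 48 hours of leaving the study", and "All Week 12 study procedures will be completed at the time of the early termination visit".

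**Outcome schedule.** In Study Procedures, blinded assessors "will assess patients monthly (week 0, 4, 8, and 12"). QEEGs fall at weeks 0, 1, 2, 8 and endpoint.

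**Course of remission.** The Background says that many patients who eventually remit "do not do so until the second 6 weeks of treatment".

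**SAP.** Its Methods describe a completer analysis and state that it is not intention-to-treat. It does not define a completer, give the week at which response was read, or say how termination-visit scores were used. Its cut-off is a reduction of 50% or more, whereas the protocol requires more than 50%.

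**The concern.** Primary Aims 1 and 2 both rest on the responder label. Under the protocol rule that label mixes week-12 outcomes with outcomes read at whatever week a patient left. Two problems follow. Prediction needs the outcome to come after the predictor, and for an exit around week 2 it does not. Also, a patient read early may be labelled a non-responder only because too little time has passed.

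The SAP route avoids the mixed timing if completers are those who finished 12 weeks. It then loses patients, and perhaps not at random. Both routes affect the effect-size estimates that the protocol gives as the purpose of this pilot. A later HAMD-17 on leavers would show how much either route matters, but none is described.

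**Working it through.** **1. When can the outcome be read?** The definitions of response and endpoint, together with the exit-visit rule, set no minimum time.

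| Exit | Outcome under the protocol rule | Relation to the week-2 QEEG |
|---|---|---|
| Before week 2 | Exit visit | No scheduled week-2 QEEG; may not enter Hypothesis 1 |
| About week 2 | Exit visit | Coincides with it |
| Week 3 | Exit visit | About one week later |
| Week 6, does not return | Last scheduled blinded HAMD-17 is week 4; handling not stated | Two weeks later |
| Before week 4, does not return | No scheduled post-baseline blinded HAMD-17; handling not stated | None |
| Completes | Week 12 | Ten weeks later |

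**2. Protocol rule: shrinkage of the responder versus non-responder difference.** Assumptions not in the documents: true week-12 response r = 50%, a fraction p leaves, leaving is unrelated to response or QEEG, every leaver reads as a non-responder, and every leaver has the QEEG. In an arm of 15 there are 7.5 true responders and 7.5 true non-responders, and 7.5p true responders move across. The share of true responders in the observed non-responder group is 7.5p / (7.5 + 7.5p) = p / (1 + p), and the mean difference shrinks by that share.

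- p = 10%: 0.75 / 8.25 = 9%
- p = 20%: 1.5 / 9.0 = 17%
- p = 30%: 2.25 / 9.75 = 23%

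Varying the inputs:

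- If 25% of leavers already read as responders at exit, all of them true responders, 3.75p move across. The shrinkage is 0.5p / (1 + 0.5p) = 5%, 9% and 13%.
- With every leaver read as a non-responder, the general form is rp / (1 − r + rp). For r = 40% it gives 6%, 12% and 17%; for r = 60% it gives 13%, 23% and 31%.

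**3. Protocol rule: response rate.** With 50% among stayers and 0% to 25% among leavers at exit, the rate is 0.5(1 − p) + p × (0 to 0.25). That is 45–47.5%, 40–45% and 35–42.5% for p = 10%, 20% and 30%, against 50% in completers.

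**4. Completer rule: power.** The protocol states power of 0.80 at 34 per group, 0.76 at 30 and 0.47 at 15, without alpha or effect size. Assume two-sided alpha 0.05 and a normal approximation. Solving from 34 per group gives d = (1.960 + 0.842) / √(34/2) = 0.68. Power is then Φ(d√(n/2) − 1.960), which gives 0.749 at 30 and 0.461 at 15. Both are within two points of the stated figures, so those figures are consistent with one another; the effect size itself is not verified.

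| Leaving | Left of 15 | Power |
|---|---|---|
| 0% | 15 | 0.46 |
| 10% | 13.5 (13 to 14) | 0.41 to 0.44 |
| 20% | 12 | 0.38 |
| 30% | 10.5 (10 to 11) | 0.33 to 0.36 |

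These use the protocol's own basis of 15 per group. The CBT comparison of responders with non-responders divides one arm of 15, so its power is lower still: at the same d, about 0.26 for a 7:8 split, 0.22 for 6:6 and 0.19 for 5:5.

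**The case against.** A reader might infer several stronger things that the documents do not support.

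- **That stopping treatment means leaving the study.** The exit wording is always about the study. Nothing says that stopping escitalopram or CBT ends participation, and in the drug arm the clinician records days without medication while the patient remains in the study. What stands is that the two events are not distinguished and no off-treatment follow-up to week 12 is described.
- **That early leavers are counted as non-responders.** No rule imputes this. A leaver who has improved by more than 50% at the exit visit is a responder. Only the tendency stands, and it rests on the protocol's own remark about late remission.
- **That nothing is collected after exit.** Adverse events are followed to resolution (Protocol IX). The gap concerns the HAMD-17.
- **That the SAP's results mix outcome times.** If completers are those who finished 12 weeks, they do not. Because the term is undefined, mixed timing can be neither asserted nor ruled out.

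The 9% to 23% is also a worst case for leavers' exit scores, and it counts leavers before week 2 who may never enter Hypothesis 1. It applies only to the protocol rule. If leaving really is unrelated to response, as step 2 assumes, the completer analysis loses patients without gaining bias from response-related dropout; the selection harm is therefore possible but not quantified.

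Finally, a week-12 score taken weeks after CBT stopped, perhaps on another treatment, answers a somewhat different question from Aim 1. That objection is fair, and it is why the off-treatment score should not be the only reading.

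**Conclusion.** The concern holds in this limited form. The protocol lets outcome time vary among early leavers and, around week 2, lets outcome and predictor coincide. The SAP's undefined completer analysis does not match the protocol's endpoint rule. Neither document separates stopping treatment from withdrawing from assessment or describes a HAMD-17 after exit.

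The size is illustrative, since the documents give no dropout or response rate. With 10% to 30% leaving and 50% true response, the protocol-rule difference shrinks by at most about 9% to 23% if leaving is unrelated to response; the bound moves with the true response rate. Under the completer rule, power falls from about 0.46 to 0.33–0.44 on the protocol's basis of 15 per group. The study is a declared, underpowered pilot, so what is at stake is mainly the effect sizes carried into a larger trial.

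**What to change.** 1. **Safety Data and Study Endpoints (Protocol V and VI).** Distinguish stopping the assigned treatment from declining further assessment. Patients who stop escitalopram or CBT but agree to stay keep the blinded HAMD-17 visits at weeks 4, 8 and 12 and the scheduled QEEGs, with the date of last dose or session recorded. The 48-hour exit visit is for those who decline further assessment. This concerns assessment only and changes no rule on when treatment stops.
2. **Aim 1.** Accept as outcome only a blinded HAMD-17 obtained after the week-2 QEEG.
3. **Protocol VI and SAP Methods.** Reconcile them: set Week 12 as the response time point, define completer, and use one cut-off (more than 50%, or 50% and more). Report results both with all available Week 12 scores, flagging those taken off treatment, and with completers only.

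**Cost.** A short protocol and consent amendment and a few sentences in the SAP, using existing assessors, visits and instruments. The small downside is that some scores will be off treatment and need a flag.

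**If follow-up has ended.** The SAP is dated 12/7/2017 and written in the past tense, so this may be the case. Item 1 could not then recover scores that were never taken. Items 2 and 3 still apply, with leavers listed by exit week and the week at which each response label was read.
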